2.0 Background

2.1 Significance of Research Question/Purpose:

Sepsis is defined as life threatening organ dysfunction caused by a dysregulated response to infection. Sepsis and septic shock, the latter defined as persistent hypotension refractory to volume resuscitation and requiring vasopressor therapy to maintain adequate blood pressure, are common reasons for admission to the intensive care unit¹. It is estimated that approximately 1 million Americans are diagnosed every year². Despite concerted efforts focused on early recognition and stabilization of septic patients, mortality rates of patients admitted with septic shock remain high at 25%-50%¹ and survival is still associated with significant comorbidity³. This is of particular importance when sepsis-associated organ failure is prolonged, as the extended recovery period keeps patients vulnerable to adverse effects associated with prolonged ICU stays (e.g., myopathy, delirium). All of this highlights the need for novel effective therapies.

The main tenets of therapy in sepsis have been focused on early recognition, hemodynamic stabilization (correction of low blood pressure) and antimicrobial therapies. This involves early aggressive fluid resuscitation and vasopressor therapy (medications such as epinephrine which increase blood pressure), as well as early empiric antibiotic therapy and effective source control, the latter of which consistently correlates with survival^{1,3,4}. Over the last two decades, most efforts to improve outcomes in sepsis have focused on resuscitation at the systemic level (e.g. blood pressure and cardiac output goals). Unfortunately, although several 'targeted' systemic resuscitation studies have shown promise during early studies (e.g. early goal directed therapy protocol⁵, large-scale confirmatory studies of these treatments have been disappointing⁶⁻¹⁰). As a result, renewed attention has shifted towards identification of sepsis-induced abnormalities at the cellular and microcirculation level, such as dysfunction of mitochondria (the parts of cells which generate energy), endothelium (the lining of blood vessels which plays a role in controlling blood supply to tissues) and cellular oxygen metabolism despite adequate tissue blood supply¹¹.

Therapies aiming to correct oxygen metabolism, mitochondrial, and endothelial dysfunction have been dubbed “metabolic resuscitation”^{12,13}.

2.2 Preliminary Data:

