3.0 Study Endpoints/Events/Outcomes

3.1 Primary Endpoint/Event/Outcome:

First outcome endpoint for Specific Aim 1: all-cause mortality measured at ICU discharge.

Second outcome endpoint for Specific Aim 1: all-cause mortality measured at 28 days post Day 0.

3.2 Secondary Endpoint(s)/Event(s)/Outcome(s):

Outcome endpoint for Specific Aim 2: Difference in clinical outcomes between both groups at ICU discharge. Specific secondary endpoints may include, depending on power and final enrollment:

- a. Duration of vasopressor therapy post administration of Vitamin C (or placebo). Conclusion of vasopressor therapy will be defined as the time point when pressors are stopped, following which they are not restarted for 24 hours.
- b. Duration of ICU stay post administration of Vitamin C (or placebo).
- c. Time to lactate clearance post administration of Vitamin C (or placebo). Time of lactate clearance will be defined as the first time point at which measured lactate level drops below the normal level as defined by the measuring laboratory.
- d. Rate of lactate and procalcitonin clearance over 24, 48 and 96 hours following Vitamin C (or placebo) administration (in patients for whom values are available). Defined as the change in lactate and procalcitonin level from the initial measurement to the measurement at the designated time point if available, or closest measurement within 4 hours of the designated time point.
- e. Duration of mechanical ventilation post administration of Vitamin C (or placebo). Cessation of mechanical ventilation will be defined as the time of extubation following which re-intubation is not required for a full 24 hours.
- f. Incidence of need for renal replacement therapy during the 96 hour drug administration period
- g. Change in serum creatinine at 24, 48, 72, and 96 hours after Vitamin C (or placebo) administration compared to level at enrollment (in patients for whom values are available). The measurement closest in time to the designated time-point (within 12 hours) will be used. Patients who are dialysis-dependent at baseline or are currently receiving renal replacement therapy will be excluded from this endpoint.
- h. Change to SOFA and/or APACHE scores from initiation of Vitamin C (or placebo) as measured at 24, 48, 72, and 96 hours.

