16.0 Data Management

16.1 Data Analysis Plan:

Patient baseline characteristics will be summarized and presented using means and standard deviations for continuous variables and frequencies and percentages for categorical variables. Treatment groups will be compared using two-sample t test for continuous variables and Chi-square test for categorical variables.

Analysis plan for Aim 1: Mortality rates between treatment groups will be compared using Chi-square test. Logistic regression model will be used to model the probability of death. Model will include treatment group and covariates determined by the investigators to impact mortality and/or those that are significantly different between groups at baseline.

Analysis plan for Aim 2: Clinical outcomes at ICU discharge will be compared between groups using two-sample t test for continuous variables and Chi-square test for categorical variables. Multivariate linear and logistic regression analysis will be performed for continuous outcomes and dichotomous outcomes respectively to adjust for covariates.

Analysis plan for Aim 3: Correlation analysis will be conducted to examine the association between clinical characteristics and Vitamin C responsiveness.

Intention-to-treat analysis will be used. Analysis will be performed using Statistical Analysis Software (version 9.3, SAS Institute Inc., Cary, NC).

16.2 Power Analysis:

The trial will enroll enough participants to demonstrate a 20% mortality difference in between treatment groups. Based on this information, 124 patients, 62 patients in each arm, would be needed to have an 80% power to detect a 20 % decrease in hospital mortality between the two groups with a two-tailed alpha error of 0.05. To account for potential dropout of participants, planned enrollment will be 70 per arm, 140 total.

16.3 Data Integrity:

REDCap™ data will be periodically reviewed by the regulatory specialist and project manager or coordinator; to occur at the request of the PI and before final analysis occurs. Standard data quality checks will be run using REDCap™'s integrated programs.

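### The renal replacement therapy endpoint (item f) has no rule for death or comfort care before dialysis, so the crude comparison can lean against the arm with fewer early deaths

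*Combined protocol and SAP*

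**What the plan says.** Section 3.2, item f, reads "Incidence of need for renal replacement therapy during the 96 hour drug administration period". It belongs to a list introduced by "Specific secondary endpoints may include, depending on power and final enrollment", so it is an optional secondary endpoint.

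Section 16.1 sets the Aim 2 analysis: "Clinical outcomes at ICU discharge will be compared between groups using two-sample t test for continuous variables and Chi-square test for categorical variables". The adjusted analysis follows: "Multivariate linear and logistic regression analysis will be performed for continuous outcomes and dichotomous outcomes respectively to adjust for covariates". On the analysis set it says "Intention-to-treat analysis will be used".

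Section 2.1 states that "mortality rates of patients admitted with septic shock remain high at 25%-50" percent. Section 16.2 says "The trial will enroll enough participants to demonstrate a 20% mortality difference in between treatment groups", and then describes that difference as one in hospital mortality. Sections 4.2 and 13.1 foresee transition to comfort care and have the infusion stopped when it happens.

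No section says how item f counts a participant who dies or moves to comfort care before RRT. There is no composite with death, no competing-risk method and no count of days alive without RRT. Items d and g are limited to participants with available values; item f is not. Item g leaves out participants who are dialysis-dependent at baseline or already on RRT; item f does not.

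**The concern.** A yes/no count over a fixed window, with all randomised participants in the denominator, leaves a death without RRT as a non-event. It is then pooled with participants whose kidneys recovered, although some of those who die early would have gone on to RRT. Comfort care before RRT works in the same way.

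This would matter little if early death were equally frequent in both arms. The trial's hypothesis is that it is not. If Vitamin C keeps people alive through the first four days, those people remain at risk of RRT and add to its count. If it causes early deaths, the count falls.

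The kidney is a safety topic in this protocol: section 14.1 discusses oxalate nephropathy. Under section 18.2 the DSMB receives the Aim 2 clinical endpoints. A reader who takes the RRT row by itself could draw the wrong direction from it.

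**Working it through.** **The plan's own figure.** Section 16.2 gives 62 per arm for 80% power at two-sided 0.05, but no control rate. Assume 30% versus 10% mortality, pooled variance and no continuity correction:

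n = [1.96·√(2·0.20·0.80) + 0.842·√(0.30·0.70 + 0.10·0.90)]² / 0.20² = (1.109 + 0.461)² / 0.04 ≈ 61.6, so 62 per arm (power 80.3%).

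A relative reduction of 20% would need 388 to 1,094 per arm for control rates of 50% to 25%. The 20% is therefore a difference of 20 percentage points. Item f has no power calculation of its own.

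**Inputs not in the documents.** The 96 h risk of death before RRT (d) and the RRT risk (r) are both assumptions.

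**Case 1: independent risks, the same RRT hazard in both arms.** With hR = −ln(1−r) and hD = −ln(1−d), constant over 96 h:

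observed RRT = hR/(hR+hD) × [1 − (1−r)(1−d)]

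Example with r = 20%, d = 20% versus 10%:
- Control: 0.2231/0.4463 × 0.36 = 18.0%.
- Fewer deaths: 0.2231/0.3285 × 0.28 = 19.0%.
- The shift is 1.0 point with no effect on the kidney.

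For r from 10% to 40%:

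| Early death, control v treated | Excess RRT in the arm with fewer deaths |
|---|---|
| 10% v 5% | 0.3 to 0.9 points |
| 20% v 10% | 0.5 to 1.9 points |
| 30% v 10% (all 20 points within 96 h) | 1.1 to 4.0 points |

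**Case 2: half of the extra survivors start RRT.** With b the RRT risk among the other survivors:

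control = (1−d0)·b; treated = (1−d0)·b + (d0−d1)·0.5

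| d0 v d1 | b | RRT, control v treated | Shift | RRT or death, control v treated |
|---|---|---|---|---|
| 10% v 5% | 20% | 18.0% v 20.5% | 2.5 points | 28.0% v 25.5% |
| 20% v 10% | 20% | 16% v 21% | 5 points | 36% v 31% |
| 20% v 10% | 30% | 24% v 29% | 5 points | 44% v 39% |

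**Against sampling error.** For 18.0% versus 20.5% at 62 per arm, SE = √[(0.18·0.82 + 0.205·0.795)/62] = 7.1 points. Across the case 2 rows shown, the shift is about 0.35 to 0.7 SE.

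In case 1 the chance of a significant Chi-square result against the arm with fewer deaths is about 3% to 7%; with no shift it would be 2.5% in that direction. For 16% versus 21% in case 2, the null SE is √(2·0.185·0.815/62) = 6.97 points and the SE under the alternative 6.96, so the chance is Φ[(5 − 1.96·6.97)/6.96] ≈ 11%.

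**Can the sign change?** Take a true 10% reduction in RRT hazard with r = 30%. Without deaths the risks are 30.0% and 1 − 0.7^0.9 = 27.5%, a benefit of 2.5 points. With early death of 20% versus 10%, the case 1 formula gives 27.1% versus 26.1%, so the benefit shrinks to 0.9 points. With 30% versus 10% it gives 25.5% versus 26.1%, a slight apparent harm.

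**The case against.** - **The documents do not state the scoring.** A reader might infer that the plan scores early deaths as RRT-free. It does not say so; that is only the default reading of an incidence, a Chi-square test and intention to treat. Because need is undefined, someone who dies in renal failure without dialysis could be counted either way. This stands, and it is why the point concerns a missing rule.
- **The powered difference is not the early-death difference.** A reader might carry the 20 points straight into item f. The power section speaks of hospital mortality; only deaths within 96 h and before RRT matter here, and someone who starts RRT and then dies is already an RRT event. This stands. The case with all 20 points inside 96 h is an upper bound.
- **The size depends on who the extra survivors are.** Shifts of 2.5 points or more for a 5 to 10 point early-death difference need survivors at high renal risk. With independent risks the shift is at most about 2 points. This stands, so both cases are shown.
- **Kidney harm would not simply be hidden.** Mortality is the primary endpoint and reaches the DSMB together with the clinical endpoints, and creatinine and SOFA are also listed. This largely stands, although those measures are themselves affected by death.
- **A composite is no clean remedy.** In case 2 it shows a benefit that comes from deaths alone. It can also mask harm: for 20% versus 10% deaths and b = 20%, add a true 5-point RRT harm. Treated becomes 21% + 5% + 10% = 36%, against 16% + 20% = 36% in control. It also misses participants moved to comfort care who die after 96 h. This stands, and rules out replacing the RRT count with the composite.

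None of this supplies the missing rule or reverses the direction of the lean.

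**Conclusion.** The gap is real and modest. Item f leaves death and comfort care before RRT unscored, and the default count leans against the arm with fewer early deaths.

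For an assumed early-death difference of 5 to 10 points, the lean is about 0.3 to 2 points under independence and 2.5 to 5 points if half of the extra survivors start RRT. It reaches 4 points under independence only if the whole 20-point mortality difference falls within 96 h. The SE is about 7 points when RRT is near 20%. All of this rests on assumed RRT and 96 h death rates.

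The documents do not support reading this as a likely false significant finding or as a threat to the primary result. The risk is a misleading direction in an optional secondary endpoint. That is worth correcting because the correction is cheap.

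**What to change.** In section 3.2, item f, and the Aim 2 paragraph of section 16.1, before unblinding:

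1. Define item f as new RRT started within 96 h, in place of the undefined need. Leave out participants who are dialysis-dependent at baseline or already on RRT, as item g does.
2. Report new RRT or death within 96 h beside it, with the same Chi-square test.
3. Tabulate four mutually exclusive rows by arm: new RRT; death before RRT; comfort care before RRT and alive at 96 h; alive without RRT or comfort care.
4. State that no kidney conclusion will be drawn from the RRT count or the composite alone.

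The cost is a few sentences and table rows. Deaths are already collected and charts are reviewed daily to Day 4; the date of a move to comfort care may need its own field if the case report form lacks one. The downside is a composite partly driven by death that can mask a kidney effect, so it must be read with its components.

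### The creatinine-change endpoint has no rule for renal replacement therapy started after enrolment, so it can understate, hide or reverse a kidney difference between arms

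*Combined protocol and SAP*

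**What the plan says.** Section 3.2 lists two renal endpoints next to each other.

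- Item f: "Incidence of need for renal replacement therapy during the 96 hour drug administration period".
- Item g: "Change in serum creatinine at 24, 48, 72, and 96 hours after Vitamin C (or placebo) administration compared to level at enrollment". It is assessed "in patients for whom values are available", and the value is chosen as follows: "The measurement closest in time to the designated time-point (within 12 hours) will be used". The renal exclusion reads: "Patients who are dialysis-dependent at baseline or are currently receiving renal replacement therapy will be excluded from this endpoint".

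Item g does not refer to item f. It gives no reference time for *currently*, and no rule for creatinine drawn after RRT has begun or for participants who die before a time point.

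The list is introduced as optional: "Specific secondary endpoints may include, depending on power and final enrollment". For analysis, section 16.1 says "Clinical outcomes at ICU discharge will be compared between groups using two-sample t test for continuous variables", adds covariate-adjusted linear regression, and states "Intention-to-treat analysis will be used". Its wording refers to ICU discharge, while item g is measured at fixed hours. I take the t test to apply to item g, because no other test is given for continuous secondary outcomes. Section 16.1 has no rule for RRT, death or missing values.

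**The concern.** Dialysis removes creatinine from the blood. Once RRT starts, a falling creatinine reflects the machine rather than the kidney. Item f shows that the plan expects some participants to start RRT within the 96 hours, yet item g takes the nearest available value whether or not it was drawn on dialysis. The two possible meanings of *currently* each cause a problem:

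- **Status at enrolment.** Participants who start RRT later stay in the analysis with creatinine lowered by dialysis. Their kidney failure can appear as improvement or as a smaller worsening.
- **Status at measurement.** The same participants leave the analysis because of something that happened after randomisation, which conflicts with intention to treat.

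Under both meanings, participants who die before a time point contribute nothing there. That adds to the distortion if mortality differs by arm, which is what Aim 1 hypothesises.

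Item g is the only continuous endpoint in section 3.2 that is specifically renal. Section 14.1 mentions oxalate nephropathy among reported events with vitamin C, and section 18.2 sends the Aim 2 clinical endpoints to the DSMB. A misleading creatinine comparison could therefore colour the renal safety reading as well as the efficacy report.

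**Working it through.** **The plan's own figure.** There is none to reproduce. The documents give no RRT rate, creatinine mean or SD, and no power for item g. The numbers below are assumptions that show direction and rough size. Only the 62 per arm comes from the plan (section 16.2).

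**Formula.** Let pA and pP be the proportions starting RRT in the active and placebo arms. Let u be their mean creatinine change had they not been dialysed, and m the mean change actually recorded on dialysis. Take mean change in all other participants as 0 in both arms, and u and m as equal across arms.

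- True difference = (pA - pP) x u
- Observed difference with dialysed values used = (pA - pP) x m
- Bias = (pA - pP) x (m - u)
- Observed difference with RRT participants excluded = 0

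If pA = pP, all of these are 0, so under these assumptions the bias needs unequal RRT use. It can also arise with equal use if dialysis changes creatinine differently in the two arms. If 0 < m < u, harm is understated; if m = 0, it is hidden; if m < 0, its sign is reversed.

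**Illustration 1: pA = 20%, pP = 10%, u = +1.5 mg/dL.** With 62 per arm this is about 12 v 6 participants (62 x 0.20 = 12.4; 62 x 0.10 = 6.2).

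| Handling | Active mean | Placebo mean | Difference | Bias |
|---|---|---|---|---|
| No dialysis effect (true) | 0.20 x 1.5 = +0.30 | 0.10 x 1.5 = +0.15 | +0.15 | – |
| Dialysed values read -1.5 | 0.20 x (-1.5) = -0.30 | 0.10 x (-1.5) = -0.15 | -0.15 | -0.30 |
| Dialysed values read 0 | 0 | 0 | 0 | -0.15 |
| RRT participants excluded | 0 | 0 | 0 | -0.15 |

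**Illustration 2: pA = 30%, pP = 10%, u = +2.0 mg/dL, SD 0.8.** A simulation of 4,000 trials with 62 per arm and a t test at two-sided 0.05 gave the percentages below.

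- True difference: 0.20 x 2.0 = +0.40. Harm is detected in about 50% of trials.
- Dialysed values averaging -0.5: 0.20 x (-0.5) = -0.10. About 11% of trials show a significant apparent benefit.
- Dialysed values averaging +0.5: 0.20 x 0.5 = +0.10. Harm is detected in about 10% of trials.
- RRT participants excluded: 0. Harm is detected in about 3% of trials, roughly the chance rate in one direction.

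With 20% v 10% and u = +2.0, the true difference is +0.20, and dialysed values averaging -0.5 to +0.5 give -0.05 to +0.05.

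**The case against.** **Enrolment status is the natural meaning.** The exclusion sentence pairs *currently* with baseline dialysis dependence, and the endpoint is a change from the enrolment level. This is fair, and on that meaning nobody is removed after randomisation for starting RRT. But dialysed values then enter the t test unmarked, so a gap remains.

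**New RRT and deaths are not lost.** Item f counts RRT over the same period, item h follows organ failure through SOFA and/or APACHE, and both primary endpoints record death. This stands. A reader might infer that the plan ignores dialysis started after enrolment; it does not. The fault is narrower: item g is not tied to item f, so the two can point in opposite directions with no rule for reading them together.

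**Bias is not automatic.** This stands too. A reader might infer that failing kidneys will always be scored as improvement, or that the arm comparison is biased whatever happens. The documents support neither. A dialysed value may still exceed the enrolment value, and with equal RRT use and effect the between-arm difference in the illustration is 0, although the change within each arm is still distorted.

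**The safety argument can be pressed too far.** Section 14.1 describes nephropathy in one transplant recipient and cites studies against a role in oxalate stones. Section 9.2 excludes people with past nephrolithiasis and a closely similar dialysis group, and section 18.2 collects all adverse events. Renal safety therefore does not rest on item g alone.

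**The endpoint is minor.** It is one of several optional secondary endpoints. That limits the importance of the point without removing it.

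**Conclusion.** The concern holds in a limited form. Item g leaves the timing of the RRT exclusion open and has no rule for RRT started after enrolment. Followed as written, it either treats dialysis-lowered creatinine as the kidney outcome or drops participants on a post-randomisation event. The comparison is biased when RRT use, or its effect on creatinine, differs by arm, and differential mortality adds to this.

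The size cannot be derived from the documents. Under the first set of assumptions, a true +0.15 mg/dL harm is observed as anything from -0.15 to 0. The 0.30 mg/dL in that illustration is the bias, and it would be wrong to read it as the apparent advantage of the worse arm, which is 0.15 in the extreme case and 0 otherwise. The extreme case also needs an enrolment creatinine above 1.5 mg/dL.

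The primary mortality result is unaffected and item f still counts new RRT. The point should be settled before unblinding, because choosing a meaning of *currently* afterwards could change the direction of the creatinine result.

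**What to change.** Amend item g and section 16.1 as follows.

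1. Define the exclusion by RRT status at enrolment only.
2. Do not use creatinine measured after the start of RRT as the outcome.
3. Give participants with new RRT the worst rank at every time point after it starts, rank the others by observed change, and compare arms with a rank test.
4. Report item f and the number of deaths by each time point, by arm, next to the creatinine result.
5. Keep mean change in mg/dL as a supportive summary, with its handling of RRT stated.

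A rank that also includes death, or a 96-hour composite of death, new RRT or doubled creatinine, could be a sensitivity analysis. Either asks a different question from item g, so neither is needed to close the gap.

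The cost is revised wording and slightly more programming, using data already to be collected. There are no extra visits, samples or participants and no change in care. The downside is that a rank result is harder to read in mg/dL, which the supportive mean partly offsets.

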- i. Total intravenous fluid administered from presentation until various intervals (3 hours, 6 hours, and 24hours), until resolution of shock, and from Vitamin C (or placebo) administration until resolution of shock.
- j. Effect of standard of care medications including corticosteroids as a sub-group analysis.

Outcome endpoint for Specific Aim 3: In general, clinical and biochemical characteristics associated with Vitamin C responsiveness will be examined. Specifics include:

- a. Assessment of whether time from onset of septic shock to receipt of Vitamin C (or placebo) influences effectiveness of Vitamin C therapy.
- b. Treatment effects as associated with or without initial presentation of inflammatory response

- Fever versus hypothermia
- Leukocytosis versus leukopenia
- Surgical versus medical source control
- c. Biobanking of blood specimens for future assessment of:
 - Vitamin C levels
 - Cytokine and chemokine levels
 - Danger associated molecular patterns (DAMPs)
 - Markers of necroptosis (RIP1 and RIP3)
 - Mitochondrial DNA and RNA for gene expressions
 - Genetic features favorable to Vitamin C therapy

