5.0 Procedures Involved

5.1 Study Design:

This is a multi-site, randomized, double-blind, placebo-controlled trial comparing a regimen of moderate-dose (6000 mg per day) Vitamin C supplementation versus placebo for the treatment of patients presenting to the ICU with septic shock. Both groups will continue to receive all other standard of care measures for septic shock as clinically indicated. Groups will be enrolled and receive study drug/placebo for 4 days (96 hours) or until 24 hours post-last pressor dose, whichever is sooner.

5.2 Study Procedures:

When a potentially eligible participant is identified, the PI or other clinical research team member will approach the individual with floor staff permission and coordination to explain the research.

PROTOCOL TITLE: Evaluating Vitamin C in Septic Shock: A Randomized Double Blind Control
Trial

VERSION DATE: March 17, 2020

After signing the consent and completing eligibility procedures, IDS will be notified. IDS will perform randomization and dispense appropriate study drug/placebo infusion materials.

Infusions must be started within 24 hours post-presentation of septic shock. Those participants who consent but cannot start an infusion within 24 hours will still follow all research procedures related to data collection except for banking of biospecimens.

Participants randomized to Vitamin C will receive IV parenteral Vitamin C; with a 1000 mg bolus to start and followed by a continuous infusion at 250 mg/hr for four days or off pressors for 24 hours, whichever is sooner. Placebo will be given as a matched infusion on the same schedule.

Chart review will take place at 24 hour time periods (Day 0, 1, 2, 3, and 4).

Blood draws for biobanking will occur at Day 0, 1, and 3 (0, 24 and 72 hours), 25 mL on day 0, and then 20 mL on days 1 and 3. Patients discharged from the hospital will not undergo blood draws following discharge. Those still in the hospital, any floor or unit, will have blood drawn if clinically possible. Blood draw will be based on a convenience sample only. Blood draw will only be done when study clinician is available and when time is available for processing and transporting. Not all participants will have all, or any, blood draw done for biobanking.

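### Secondary endpoint i counts early IV fluid from presentation, so its 3 h and 6 h totals can close before study drug starts and cannot then respond to treatment

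*Combined protocol and SAP*

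**What the plan says.** Section 3.2 defines the Aim 2 endpoint as a difference in clinical outcomes between the two groups, then lists candidates under the words "Specific secondary endpoints may include, depending on power and final enrollment". Item i has two parts. The first is anchored at presentation: "Total intravenous fluid administered from presentation until various intervals (3 hours, 6 hours, and 24hours), until resolution of shock". The second is anchored at treatment: "and from Vitamin C (or placebo) administration until resolution of shock". Section 16.1 compares continuous Aim 2 outcomes by two-sample t test and adds covariate-adjusted regression, without naming the covariates.

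Section 5.2 allows up to 24 h from presentation of septic shock to the start of infusion. Notes 2 and 3 to the section 5.3 schedule give the same limit from identification. Note 1 defines identification as shock onset for patients already in hospital and otherwise as arrival at the hospital or emergency department. The steps before infusion are sequential: "After signing the consent and completing eligibility procedures, IDS will be notified", and then "IDS will perform randomization and dispense appropriate study drug/placebo infusion materials". Section 9.1 also requires that hypotension needing vasopressors persist after at least 30 mL/kg of fluid.

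Most of the list follows a treatment clock. Items a to e, g and h time their follow-up from study-drug administration; item h, for example, reads "Change to SOFA and/or APACHE scores from initiation of Vitamin C (or placebo) as measured at 24, 48, 72, and 96 hours". Items d and g do take their starting value from an initial or enrolment measurement.

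**The concern.** Fluid given before study drug cannot be changed by study drug. If a window closes before the infusion begins, a between-arm test of that total compares a baseline quantity, and any difference is chance. If the window straddles the start, the treated part is mixed with untreated fluid and a real effect is diluted.

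The protocol itself expects the delay to differ between patients, since Aim 3 item a is "Assessment of whether time from onset of septic shock to receipt of Vitamin C (or placebo) influences effectiveness of Vitamin C therapy". Fluid requirement is also a natural outcome for this drug: section 2.2 cites reduced resuscitation volume in burn patients as part of the rationale. At stake is the reading of the early totals. A null result at 3 h or 6 h could be taken as no fluid-sparing effect when the measure had little chance to show one, and a nominally significant result could be largely baseline imbalance.

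**Working it through.** The documents give no SD, expected effect or power for the fluid totals, so there is no plan figure to reproduce. The check is on timing.

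**Inputs from the documents.** Windows W = 3, 6 and 24 h from presentation (section 3.2, item i). Permitted start S = 0 to 24 h (section 5.2; section 5.3, notes 2 and 3).

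**Step 1: a given start time.** The share of the window after study-drug start is max(0, W − S)/W.

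| Start S | 3 h window | 6 h window | 24 h window |
|---|---|---|---|
| 1 h | 66.7% | 83.3% | 95.8% |
| 3 h | 0% | 50% | 87.5% |
| 6 h | 0% | 0% | 75% |
| 12 h | 0% | 0% | 50% |
| 24 h | 0% | 0% | 0% |

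This step needs no assumption about the distribution of start times.

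**Step 2: a range of start times.** The distribution of S is not stated. Assume S uniform on 0 to U, with U = 6, 12 or 24 h.

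- Share of patients with no treated time in the window: max(0, 1 − W/U). Example: W = 3, U = 12 gives 1 − 3/12 = 75%.
- Mean treated share of the window, with m = min(W, U): (mW − m²/2)/(UW). Examples: W = 3, U = 6 gives (9 − 4.5)/18 = 25%; W = 24, U = 12 gives (288 − 72)/288 = 75%.

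| Starts over | No treated time: 3 h / 6 h | Mean treated share: 3 h / 6 h / 24 h |
|---|---|---|
| 0-6 h | 50% / 0% | 25% / 50% / 87.5% |
| 0-12 h | 75% / 50% | 12.5% / 25% / 75% |
| 0-24 h | 87.5% / 75% | 6.25% / 12.5% / 50% |

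Counted from study-drug start, the treated share is 100% in all three windows for every participant who starts.

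**Step 3: what dilution does to a test (illustration only).** Take 62 per arm (section 16.2) and two-sided alpha 0.05. A standardised effect d = (1.960 + 0.842) × √(2/62) = 0.503 has 80% power on a fully treated window. Assume the effect shrinks in proportion to the mean treated share and the SD stays the same. The chance of a significant result in the correct direction is then Φ(2.802 × share − 1.960):

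- 3 h window: 4% (starts over 0-24 h), 5% (0-12 h), 10% (0-6 h).
- 6 h window: 5%, 10%, 29%.
- 24 h window: 29%, 56%, 69%.

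The shares in steps 1 and 2 are of time, not of fluid volume. Because at least 30 mL/kg must come before eligibility, the volume share after study-drug start could be smaller, but the documents do not let one compute it.

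**The case against.** **The consequence is small.** The item is one optional secondary endpoint, it already contains a treatment-timed total, and nothing in the primary analysis, sample size or safety review depends on it. This stands and sets the weight of the point. The existing total does not fully replace the early ones, because it has no fixed duration.

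**The presentation-anchored totals may be meant as description.** Item j, next in the list, is a subgroup analysis rather than an outcome, and the section 16.1 sentence refers to outcomes at ICU discharge, which suits a 3 h total poorly. That reading is possible. However, nothing labels these totals as descriptive, and they sit under a between-group endpoint.

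**The percentages rest on assumed start times.** This is correct. Uniform starts from 0 h are also generous to the plan, given the steps that must come first, and the 0% for the 6 h window follows simply from capping starts at 6 h. Only step 1 is free of assumption.

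**A treatment clock is undefined for non-starters.** Section 5.2 keeps in data collection those who consent but cannot start within 24 h, and section 16.1 specifies intention-to-treat. This also stands, and the fix needs an anchor rule for them.

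**Re-timed 3 h and 6 h totals may still be insensitive.** The documents give no expected onset for a fluid effect. Re-timing makes a response possible; it does not guarantee one.

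A reader might go further and infer that the comparison is biased. The documents do not support that: assignment is randomised and blinded, so pre-treatment fluid differs between arms only by chance. Nor do they support saying that most patients will be untreated during these windows, since actual start times are not given.

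**Conclusion.** The point holds as a loss of sensitivity, mainly in the 3 h and 6 h totals. For any start at or after 3 h (or 6 h) the matching total cannot respond to treatment; this follows from the protocol's own timing. How many patients are affected is unknown: 50% to 87.5% for the 3 h window and 0% to 75% for the 6 h window, under the three uniform ranges. The 24 h total keeps 50% to 87.5% of its time after study-drug start on average, so with early starts it is little affected. The presentation-to-resolution total is diluted by an amount that cannot be computed.

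These figures take presentation and identification as the same clock. Item i does not define presentation. If it meant hospital arrival for a patient who developed shock later in the stay, the gap before study drug could exceed 24 h.

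Item i as a whole is not invalid, because its last component is correctly timed. The change is worth considering because it is cheap, not because any main conclusion depends on it.

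**What to change.** In section 3.2, item i:

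- Count the 3 h, 6 h and 24 h totals from the start of study drug or placebo. For randomised participants who never start, count from randomisation time, so that the intention-to-treat comparison keeps everyone.
- Keep the existing administration-to-resolution total, with the same anchor for non-starters.
- Report fluid from identification, as defined in note 1 to the section 5.3 schedule, to that anchor as a baseline descriptor. Do not test it as an outcome.
- Drop the separate test of the presentation-to-resolution total. On the identification clock, for a patient still in shock at the anchor, it is the sum of the baseline descriptor and the anchor-to-resolution total.

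In section 16.1, name the baseline fluid amount as a covariate in the regression for the fluid outcomes.

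**Cost.** Two short edits and re-windowing of chart fluid data. The new 24 h total lines up with the Day 1 (+24 hours) chart review; the 3 h and 6 h totals need timed chart entries, as they do now. No patient procedure changes. The main loss is that total fluid since presentation is described rather than tested. A smaller one is that starters and non-starters have different anchors, which should be stated with the results.
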